4.2 Exclusion Criteria

Individuals will be excluded from study participation if they meet any of the following criteria:

- 2. Any concomitant treatment or prior ocular procedure or surgery in either eye or alteration of the dose of systemic medications at the time of entry into the study that could interfere in the assessment of the trial, per the Investigator's judgment or per details below:
 - a. Prior history of Isotretinoin (Accutane)
 - b. Corneal refractive surgery, glaucoma surgery, or corneal transplantation within 2 years prior to Visit 1
 - c. Altered use of nutraceuticals or multivitamins throughout the study
 - d. Topical ophthalmic medications, including ocular hypotensive (glaucoma) medications, eye drops, gels, or AT (other than study-provided Refresh Plus®) throughout the study
 - f. Penetrating intraocular surgery within 12 months prior to Visit 1
 - g. Eyelid surgery or ocular surface surgery within 6 months prior to Visit 1
 - h. Altered dose of the following used on a chronic basis within 3 months prior to Visit 1:
 - Anticholinergics

[figure not shown]
- Antidepressants
- Antihistamines
- Systemic immunosuppressive agents
- Oral steroids (dose must be <11 mg prednisone or equivalent/day)
Dose must remain stable throughout study.

- i. In either eye, have had punctal occlusion (cauterization or plugs [silicone or dissolvable]) within 3 months prior to Visit 1 or anticipate new or additional punctal occlusion during the duration of the study.
NOTE: Permanent plugs lost should be replaced.
- j. Any other Investigational Product within 45 days prior to Visit 1
- k. Prescription treatments for ocular surface disease within 30 days prior to Visit 1, including
 - Topical cyclosporine (Restasis®, Cequa®)
 - Topical lifitegrast (Xiidra®)
 - Ocular corticosteroids, including but not limited to fluorometholone and loteprednol etabonate (Eysuvis®)
 - Varenicline (Tyvara®)
- l. Autologous serum within 30 days prior to Visit 1
- m. Altered dose of tetracycline compounds (tetracycline, doxycycline, or minocycline) within 30 days prior to Visit 1.
Dose must remain stable throughout study.
- n. Topical ocular antibiotics, topical ocular antihistamines or mast cell stabilizers, topical or nasal vasoconstrictors within 14 days prior to Visit 1

3. Have corneal erosive disease (e.g., confluent staining [NEI grade 4], confluent filaments) or other conditions suggestive of extensive damage of the cornea in either eye.
4. Have a history of glaucoma or IOP >25 mmHg at Visit 1 or a history of elevated IOP (>25 mmHg) in either eye.
5. Wear contact lenses for 14 days prior to Visit 1 or throughout the study.

7. Are considered legally blind in either eye (LogMAR BCVA ≥ 1.0 or Snellen BCVA $\leq 20/200$).

9. Have a history of stem cell or bone marrow transplant.

- g. Significant conjunctival scarring
- h. Chemical burn
- i. History of herpetic or neurotrophic keratitis
- j. Serious systemic disease or uncontrolled medical condition that, in the judgment of the Investigator, could confound study assessments or limit compliance.

11. Have a history of liver, renal or hematological disease that, in the judgment of the Investigator, could confound the study assessments or impact subject safety.
12. Have an allergy to any component of the study drug formulation.
13. Have a documented history of ocular allergies in either eye that, in the judgment of the Investigator, are likely to have an acute increase in severity due to the expected timing of the exposure to the allergen to which the subject is sensitive. Subjects sensitive to seasonal allergens that are not expected to be present during the study are permitted.
14. Have systemic signs of infection (e.g., fever or current treatment with antibiotics).
15. Are an employee of a site that is directly involved in the management, administration, or support of this study or an immediate family member (grandparent, parent, sibling, child) of the same.
16. Have a known history of alcohol and/or drug abuse.
17. Are an active (daily) user of tobacco or marijuana.

19. Are unwilling or unable to comply with the study protocol.

4.3 Screen Failures

Screen failures are defined as subjects who consent to participate in the clinical study but are not subsequently randomly assigned to the study intervention or entered in the study. Minimal information, including demography, screen failure details, eligibility criteria, and any serious adverse event (SAE) will be recorded.

Individuals who do not meet the criteria for participation in this trial (screen failure) at the completion of Visit 1 because of the following may be rescreened:

- Prohibited medications from which the subject may discontinue for purposes of screening eligibility (with approval from Investigator based on clinical safety).
- Exclusionary medical history status at time of screening that will change (e.g., ocular infection, surgical history duration, etc.).

Rescreened subjects will be assigned a new participant number.

5. Study Treatments or Interventions

5.1 Investigational Products

Four (4) IPs will be administered during this study:

- SY-201 Ophthalmic Solution 2.0%
- SY-201 Ophthalmic Solution 1.0%
- SY-201 Ophthalmic Solution 0.5%
- Vehicle solution

5.1.1 Description

Table 1: Active and Vehicle IPs

	Active Investigational Product	Vehicle Control (Placebo)
Product	SY-201 Ophthalmic Solution	SY-201 Placebo
Dosage form	Solution/Drops	Solution/Drops
Unit dose	 [w/v]) [w/v]) (1.0% w/v) (0.5% w/v)	 [w/v]) (0.0% w/v)
Route of administration	Topical ocular administration	Topical ocular administration
Physical description	Sterile, colorless, clear liquid	Sterile, colorless, clear liquid

5.1.2 Dosage and Administration

This study includes a run-in period in which 1 drop of single-masked vehicle will be administered OU BID over 14 days. Administration of the double-masked IP, also 1 drop OU BID, will occur over a 60-day treatment period. In both periods, administration is preferred in the morning and evening, with 8 to 12 hours between instillations.

At Visit 1 (Day -14), subjects will be assigned of single-masked run-in product vehicle and self-administer their first dose under the supervision of the site staff.

Subjects will be instructed to instill the run-in product as 1 drop into each eye. Subjects will then take home their 3 assigned kits (sufficient for up to 15 days) of run-in product for self-administration. Subjects will dose at home that evening.

The used and unused containing single-masked run-in must be returned to the site at Visit 2 (Day 1). Subjects should **not** dose run-in product the day of Visit 2.

At Visit 2, randomized subjects will be assigned 2 IP kits of double-masked IP (SY-201 Ophthalmic Solution 2.0%, 1.0%, or 0.5% or vehicle). The first dose of double-masked IP, taken from an assigned kit, will be self-administered in the clinic by the subject under the supervision of the site staff. Subjects will be instructed to instill the IP as 1 drop into each eye. Subjects will be queried on drop comfort and then take home their 2 assigned kits (sufficient for up to 10 days) of double-masked IP for self-administration. Subjects will dose at home that evening.

Subjects will return the used and unused double-masked IP at each subsequent visit (through Visit 6) and receive new kits of double-masked IP to take home at Visit 3 (2 kits, sufficient for up to 10 days), Visit 4 (4 kits, sufficient for up to 20 days), and Visit 5 (7 kits, sufficient for up to 35 days).

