	
[REDACTED]
 
g. Significant conjunctival scarring h. Chemical burn i. History of herpetic or neurotrophic keratitis j. Serious systemic disease or uncontrolled medical condition that, in the judgment of the Investigator, could confound study assessments or limit compliance.
 
11. Have a history of liver, renal or hematological disease that, in the judgment of the Investigator, could confound the study assessments or impact subject safety.
 
12. Have an allergy to any component of the study drug formulation.
 
13. Have a documented history of ocular allergies in either eye that, in the judgment of the Investigator, are likely to have an acute increase in severity due to the expected timing of the exposure to the allergen to which the subject is sensitive. Subjects sensitive to seasonal allergens that are not expected to be present during the study are permitted.
 
14. Have systemic signs of infection (e.g., fever or current treatment with antibiotics).
 
15. Are an employee of a site that is directly involved in the management, administration, or support of this study or an immediate family member (grandparent, parent, sibling, child) of the same.
 
16. Have a known history of alcohol and/or drug abuse.
 
17. Are an active daily user of tobacco or mari uana.
 
[REDACTED]
 
19. Are unwilling or unable to comply with the study protocol.

Investigational products:	SY-201 Ophthalmic Solution 2.0% SY-201 Ophthalmic Solution 1.0% SY-201 Ophthalmic Solution 0.5% Vehicle solution (run-in and vehicle)
Dosing regimen:	Both run-in and IP: 1 drop OU BID, once in the morning and once in the evening, 8-12 hours apart
Assessments/Evaluations:	Efficacy 
• tCFS (mNEI scale, 0-20) 
[REDACTED]

	
Safety
 
• AE monitoring• Safety labs (chemistry and hematology)• BCVA• Slit lamp biomicroscopy and external eye exam• IOP• Dilated ophthalmoscopy• Drop comfort assessment
Duration of study:	74 days (14 days of run-in, 60 days of treatment)

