3.1 Overall Design of the Study

This is a phase 2, multi-center, double-masked, randomized, vehicle-controlled, dose-response, parallel-group study designed to evaluate the ocular and systemic safety and ocular efficacy of SY-201 Ophthalmic Solution over a 60-day treatment period in subjects with moderate to severe DED.

During the 14-day single-masked run-in period, approximately 200 subjects will instill vehicle as 1 drop BID in both eyes (OU). At Visit 2, subjects will be randomized in a 1:1:1:1 ratio to 4 treatment groups: Vehicle (n=50) and SY-201 Ophthalmic Solution 2.0% (n=50), 1.0% (n=50), and 0.5% (n=50). Double-masked IP will be instilled as 1 drop OU BID for 60 days.

The study will consist of 6 clinic visits: Visit 1 (-14 Days, Screening), Visit 2 (Day 1, Randomization), Visit 3 (Day 7 ± 2 days), Visit 4 (Day 14 ± 2 days), Visit 5 (Day 28 ± 2 days), and Visit 6 (Day 60 ± 3 days, End of Study/Early Termination). A study schematic follows ([Figure 1](#)).

Figure 1: Study Schematic

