3.2 Rationale for the Study Design

This study will examine the ocular and systemic safety and ocular efficacy of SY-201 Ophthalmic Solution versus vehicle dosed OU BID for 60 days in subjects with moderate to severe DED.

SY-201 Ophthalmic Solution and vehicle will each be administered as a topical ophthalmic solution. In the single-masked run-in period, vehicle will be dosed OU BID by all subjects to normalize baseline conditions between subjects. Subjects will self-administer the first dose in-clinic at Visit 1 and all remaining doses at home. In the double-masked treatment period, subjects will self-administer 1 dose of IP in-clinic at Visit 2 (Day 1) and Visit 6 (Day 60) and all remaining doses at home, OU BID.

Direct instillation is the most efficient method for delivery to the ocular surface and is an accepted and widely used method for topical application to the eye. Each dose will be delivered by administering 1 drop (in each eye from a single-use vial.

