7.1.2 Randomization (Visit 2, Day 1)

The following procedures will be performed at Visit 2:

- Confirm study eligibility based on Inclusion/Exclusion criteria.
- Update CMs
- Assess AEs
- Administer the following subject-rated symptom assessments:
 - BCVA
 -
 - Biomicroscopy and external eye exam
 - OU tear collection under slit lamp for biomarker test (quantitative POC MMP-9)
 - CFS
 - **Note:** After CFS grading, wait at least 15 minutes before conducting
 -
 - IOP
 - Confirm that the subject is eligible for randomization. The trained site staff will then conduct the following procedures:
 - Enter subject information into Interactive Web Randomization System (IWRS) to determine randomization code and kit number.
 - Explain the method of IP administration. Evaluate the subject's instillation technique.
 - Dispense 2 double-masked IP kits (sufficient for up to 10 days) to the subject to take home.
 - Observe as the subject self-administers the first dose of double-masked IP at the clinic/site. All remaining doses will be administered by the subject at home, OU BID (morning and evening, instillations approximately 8-12 hours apart).

- Drop comfort assessment
- Issue AT diary and train subject in diary completion.
- Dispense preservative-free AT (Refresh Plus[®]) and counsel subject to limit AT use to ≤ 2 instillations per day.

7.1.3 **Visit 3 (Day 7 \pm 2 days)**

The following procedures will be performed at Visit 3:

- Update CMs
- Assess AEs
- Administer the following subject-rated symptom assessments:
 - BCVA
 - Biomicroscopy and external eye exam
 - SE tear collection under slit lamp for biomarker test (quantitative POC MMP-9)
 - CFS
 - IOP
 - Collect AT diary and all used and unused AT and IP.
 - Issue new AT diary.
 - Dispense preservative-free AT (Refresh Plus[®]) and remind subject to limit AT use to ≤ 2 instillations per day.
 - Dispense 2 double-masked IP kits (sufficient for up to 10 days) to the subject to take home.

7.1.4 **Visit 4 (Day 14 \pm 2 days)**

The following procedures will be performed at Visit 4:

- Update CMs
- Assess AEs
- Administer the following subject-rated symptom assessments:
 - BCVA
 - Biomicroscopy and external eye exam
 - SE tear collection under slit lamp for biomarker test (quantitative POC MMP-9)
 - CFS

- IOP
- Collect AT diary and all used and unused AT and IP.
- Issue new AT diary.
- Dispense preservative-free AT (Refresh Plus[®]) and remind subject to limit AT use to ≤ 2 instillations per day.

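### Kits dispensed at Visit 3 fall short of the longest in-window gap to Visit 4; those dispensed at Visit 5 do too if dosing runs to Visit 6

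*Protocol*

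**What the plan says.** Protocol 3.1 sets the windows: "Visit 3 (Day 7 ± 2 days), Visit 4 (Day 14 ± 2 days" and then "Visit 5 (Day 28 ± 2 days), and Visit 6 (Day 60 ± 3 days, End of Study/Early Termination".

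Protocol 5.1.2 sets the supply: two kits at Visits 2 and 3 (10 days each), four at Visit 4 (20 days), and "Visit 5 (7 kits, sufficient for up to 35 days". The visit steps repeat these figures; 7.1.2 and 7.1.3 both read "Dispense 2 double-masked IP kits (sufficient for up to 10 days) to the subject to take home".

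Leftovers do not accumulate: "Subjects will return the used and unused double-masked IP at each subsequent visit (through Visit 6".

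On how long dosing lasts, the text points two ways.

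- Protocol 5.1.2 says "Administration of the double-masked IP, also 1 drop OU BID, will occur over a 60-day treatment period", and the synopsis gives the duration as "74 days (14 days of run-in, 60 days of treatment".
- Protocol 3.2 says "subjects will self-administer 1 dose of IP in-clinic at Visit 2 (Day 1) and Visit 6 (Day 60", and the Visit 6 window runs to Day 63. Protocol 7.1.5 also tells subjects to hold back one dose on the day of Visit 6, which presumes that they are still dosing then.

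**The concern.** The supply and the visit windows were set separately and do not fit together at two of the four dispensing points. A subject who takes every dose and attends every visit in window could run out of drops. Between Visits 5 and 6 the missing doses would come in the last one or two days before the tCFS grading used for the first primary endpoint. If the vial for the clinic dose at Visit 6 comes from the same kits and all have been used, the second drop comfort assessment is lost as well.

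SAP 9.7.1.4 counts expected doses as two per day up to the last dose date. A gap caused by supply would therefore be recorded as the subject's non-compliance.

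**Working it through.** **Inputs.** Windows from Protocol 3.1: Visit 2 on Day 1, Visit 3 on Days 5–9, Visit 4 on Days 12–16, Visit 5 on Days 26–30, Visit 6 on Days 57–63. Supply from Protocol 5.1.2. Dosing is twice daily, and SAP 9.7.1.4 gives one vial per dose for both eyes, so supply in doses = 2 × days.

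**The plan's own figures.** Days per kit: 10/2 = 10/2 = 20/4 = 35/7 = 5. The kit counts agree with each other.

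**Longest gap** = latest allowed day of the next visit − earliest allowed day of the current one.

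| Interval | Nominal gap | Longest gap | Days supplied | Margin |
|---|---|---|---|---|
| V2–V3 | 7 − 1 = 6 | 9 − 1 = 8 | 10 | +2 |
| V3–V4 | 14 − 7 = 7 | 16 − 5 = 11 | 10 | −1 |
| V4–V5 | 28 − 14 = 14 | 30 − 12 = 18 | 20 | +2 |
| V5–V6 | 60 − 28 = 32 | 63 − 26 = 37 | 35 | −2 |

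All nominal gaps are covered. Of the 5 × 5 = 25 allowed V3/V4 day pairs, one exceeds supply (5/16). Of the 5 × 7 = 35 allowed V5/V6 pairs, three do: 26/62 and 27/63 (36 days) and 26/63 (37 days).

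**Doses.** Assumption, not stated in the documents: the morning dose on the day of Visits 3 and 5 comes from the old kits, and the new kits start that evening. For a gap of g days, doses needed before the next visit day = 1 + 2(g − 1).

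*V3–V4, g = 11:* 1 + 2 × 10 = 21, or 22 if the Visit 4 morning dose must also come from these kits. Supply is 20, so the shortfall is 1 or 2. The vials last through the morning of Day 15.

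*V5–V6, dosing to Visit 6:*

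| g | Before Visit 6 | With clinic dose | Supply | Total shortfall |
|---|---|---|---|---|
| 35 | 1 + 2 × 34 = 69 | 70 | 70 | 0 |
| 36 | 1 + 2 × 35 = 71 | 72 | 70 | 2 |
| 37 | 1 + 2 × 36 = 73 | 74 | 70 | 4 |

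The source of the Visit 6 clinic vial is not stated, so the doses missed depend on the reading:

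- One home vial kept for the clinic: 2 or 4 doses missed before the visit, clinic dose given.
- All vials used at home: 1 or 3 missed before the visit, and the clinic dose missed too.
- Clinic vial from separate site stock: 1 or 3 missed before the visit, clinic dose given.

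*V5–V6, home dosing ending on Day 60:* Visit 5 on Day 26 needs 1 + 2 × 34 + 1 = 70; on Day 27, 1 + 2 × 33 + 1 = 68. Supply is 70, so nothing is missed.

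**Sensitivity to the counting rule.** Suppose instead that no new vial is used on the day of Visit 3 and none of those vials on the day of Visit 4. Then V3–V4 needs 2 × 10 = 20 and is just covered. That requires both doses on the Visit 3 day to be taken before the old kits are handed in, although doses are spaced 8 to 12 hours apart. Under the same rule, a 37-day V5–V6 gap needs 2 × 36 = 72 before the clinic dose and stays short.

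**The case against.** The strongest reply concerns Visit 5 to Visit 6. The regimen is given as 60 days, and with Visit 5 as early as Day 26 the 70 vials cover every dose through the end of Day 60 with one left for the clinic. In all three short pairs the missed doses fall after Day 60, so nobody loses part of a 60-day course. This stands as far as it goes: the text is ambiguous about Days 61–63. A reader might infer that the Visit 5 supply is simply wrong, and the documents do not support that. They lean towards dosing until Visit 6, through the held-back dose and the clinic dose, but state no rule. The reply does not touch Visit 3 to Visit 4.

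Second, vials per kit are not visible, and Protocol 5.1.2, 5.2.1 and 5.2.2 have gaps where an overage or replacement-kit rule could sit. This also stands. The visible text shows no resupply rule and no maximum gap between visits, but that does not prove that none exists.

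Third, nothing in the analysis turns on it. For a subject with Visit 6 on Day 63, the SAP's expected count is 2 × 63 = 126 doses, of which 125 are due (a single dose on the last day). Missing four leaves 121/126 = 96.0%; missing two more at Visit 3 to Visit 4 leaves 119/126 = 94.4%. Both are far above the 80% category. Data after an interruption are kept (SAP 9.7.1.5.1), and there is no Per Protocol set to be excluded from (SAP 9.8.3). A reader might infer that the primary comparison is biased; the documents give no ground for that, since few doses are involved and the supply rule is common to all arms.

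Lastly, the supply limits are printed in the visit steps, so staff can book around them. That helps in practice, but no visible instruction tells them to.

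**Conclusion.** A minor conflict between two stated rules, with medium confidence. The Visit 3 supply does not cover the longest allowed gap to Visit 4: 10 days against 11, one or two doses, in 1 of 25 day pairs. The Visit 5 supply falls short by two or four doses in total in 3 of 35 pairs if dosing continues until Visit 6, and by none if it stops at Day 60.

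This takes the protocol's supply figures at face value, with new kits started on the evening of the visit and no overage or resupply rule in the redacted text. The day-pair counts are not probabilities, because the documents give no distribution of visit days. The kit arithmetic itself is sound, and the effect on the treatment contrast should be very small. The point merits action because the correction is cheap and keeps compliant, in-window subjects on drug up to the tCFS grading.

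**What to change.** In Protocol 5.1.2, 7.1.3 and 7.1.5:

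- Dispense 3 kits at Visit 3: 15 days against at most 11, or 30 doses against at most 22.
- Dispense 8 kits at Visit 5: 40 days against at most 37, or 80 doses against at most 74.
- State that dosing continues until Visit 6.

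Visits 2 and 4 need no change. The cost is at most 2 extra kits per subject, 2 × 200 = 400 in total, and a minor protocol amendment, which needs IRB review.

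Capping the gaps at 10 days (Visit 3 to 4) and 35 days (Visit 5 to 6) would need no extra supply and would leave 24 of 25 and 32 of 35 day pairs allowed. It is less clean, because visits that are now in window would become deviations. If the sponsor means dosing to end at Day 60 whatever the date of Visit 6, saying so settles Visit 5 to 6 but leaves Visit 3 to 4 short.

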5.2 Preparation/Storage/Handling/Accountability

5.2.1 Acquisition and Accountability

. The IP may be distributed by trained study staff. Used and unused IP will be maintained at the site for accountability by the clinical study monitor. When authorized by the Sponsor and after the clinical study monitor has verified drug accountability is complete and accurate, all used and unused single-masked (run-in) and double-masked IP will be returned for destruction.

5.2.2 Product Formulation, Appearance, Packaging and Labeling

Pouch labels will contain the following information: protocol number, contents, batch and pouch numbers, dosing instructions, storage temperature, Sponsor, and required statement(s) per regulatory agency.

Kit labels will contain the following information: protocol number, contents, batch and kit numbers, storage temperature, Sponsor, and required statement(s) per regulatory agency.

5.2.3 Product Storage and Stability

At clinical sites, IP will be stored in a securely locked cabinet or enclosure. Access should be strictly limited to the Investigators and their designees. Neither the Investigators nor any designees may provide IP to any subject not participating in this study. Subjects will be instructed on the proper storage of IP.

IP should be protected from light and stored inside the

5.2.4 Preparation

Neither SY-201 Ophthalmic Solution nor vehicle will require on-site preparation by the Investigator.

5.3 Measures to Minimize Bias: Randomization and Masking

To minimize bias, the treatment phase of this study is randomized and double-masked.

Subjects will be randomized to treatment assignment. If unmasking is required, the integrity of the study assessments and objectives will be maintained by limiting access to the unmasked data.

A randomization schedule will be generated by the electronic data capture (EDC) system. The EDC will be used for randomization and unmasking.

Double-masked IP—SY-201 (2.0%, 1.0%, or 0.5%) or vehicle—assigned to subjects at randomization will be identical in appearance. Sponsor, subjects, and investigative staff will be masked to the identity of treatment until completion of the study and final database lock.

Appropriate precautions must be taken to prevent unauthorized access to the randomization scheme. Unless the subject's safety requires otherwise and if time permits, the decision to unmask a treatment assignment is to be made jointly by the Investigator and Sponsor's medical monitor after consultation with the Sponsor.

